#### **4.6.2 Study Treatment Discontinuation**

Study treatment should be permanently discontinued in patients who experience any of the following:

- A DLT during the DLT window in patients enrolled in the dose-escalation phase
- Anaphylaxis, acute respiratory distress, or Grade 4 IRR
  - If a Grade 3 IRR is recurrent during the second and subsequent cycles, study treatment may be discontinued at the discretion of the investigator, following an individual benefit–risk assessment.
- Any adverse event that leads to a delay of more than 21 days in the start of the next treatment cycle

- Any hematologic adverse event that meets criteria for permanent discontinuation according to the guidelines provided in Section 5.1.8
- Hy's Law cases
- Grade  $\geq 3$  non-hematologic adverse event that has a reasonable possibility of being related to study treatment and either is life threatening or does not resolve to Grade  $< 2$  within 21 days
- Disease progression
- Pregnancy

In case of toxicity solely attributable to one drug of the combination requiring discontinuation, the other study drugs may be continued for patients experiencing clinical benefit as determined by the investigator after discussion with the Medical Monitor.

The primary reason for study treatment discontinuation should be documented on the appropriate eCRF.

Patients who discontinue study treatment will not be replaced, except as outlined below:

- During the dose-escalation phase, patients who discontinue study treatment prior to completing the DLT assessment window for reasons other than a DLT will be replaced by an additional patient at that same dose level.
- Patients who discontinue before having received at least one dose of each component of the combination will be replaced.

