## **5. ASSESSMENT OF SAFETY**

### **5.1 SAFETY PLAN**

The safety plan for patients in this study is based on clinical experience with study treatment components in completed and ongoing studies. The anticipated important safety risks of IMPs in this study (i.e., obinutuzumab, rituximab, idasanutlin, and venetoclax) are outlined below. Please refer to the Obinutuzumab, Rituximab, Idasanutlin, and Venetoclax Investigator's Brochures for a complete summary of safety information.

Several measures will be taken to ensure the safety of patients participating in this trial. Eligibility criteria have been designed to exclude patients at higher risk of toxicities (see Section 4.1). In addition, patients will undergo adequate safety monitoring during the study, as described in this section and in Section 4.5. Guidelines for managing adverse events, including criteria for dosage modification and treatment delays or discontinuation, are provided in Section 5.1.8.

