**Table 15 Idasanutlin Dose-Reduction Steps**

Initial Dose	Dose Reduction in Milligrams		
	Step 1	Step 2	Step 3
100 mg	Minus 50 mg	No further reduction a	No further reduction a
150 mg	Minus 50 mg	No further reduction a	No further reduction a
200 mg	Minus 50 mg	Minus 50 mg	No further reduction a
250 mg	Minus 100 mg	Minus 50 mg	No further reduction a
300 mg	Minus 100 mg	Minus 50 mg	Minus 50 mg
350 mg	Minus 100 mg	Minus 100 mg	Minus 50 mg
400 mg	Minus 100 mg	Minus 100 mg	Minus 50 mg

a When no further idasanutlin dose reduction is possible, the patient will be discontinued from the study.

The dose of venetoclax will be reduced by at least 25% from the current dose (rounded to the lower closest 50 mg) or return to the previous dose, with a minimum final dose of 200 mg. If the dose level reaches 200 mg, no further reduction will be allowed and the patient will be discontinued from the study.

Toxicities that occur during the cycle and subside prior to the next cycle should not trigger the suggested dose modifications. Guidelines for management of toxicities during induction treatment are provided in Section 5.1.8.1 and during consolidation or maintenance treatment in Section 5.1.8.2.

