### Non-Hematologic Toxicities during Induction Treatment

Guidelines for management of non-hematologic toxicities that occur during induction treatment are presented in [Table 18](#).

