**Table 18 Guidelines for Management of Non-Hematologic Toxicities**

Event	Action to Be Taken
General guidance for treatment delays, discontinuation, and resumption	
 
• If study treatment is withheld for > 21 days because of a toxicity that is attributable to study treatment, permanently discontinue study treatment.
 
• Permanently discontinue study treatment for Grade 4 events.
 
• When a treatment cycle is delayed because of toxicity resulting from any component of the regimen, all study treatment should be held and resumed together to remain synchronized.
 
• Dosing may be resumed after resolution to Grade <math>\leq 1</math> or baseline status. Resumption of dosing without complete resolution of toxicity may be considered in special circumstances after having obtained Medical Monitor agreement.
 

IRRs and anaphylaxis	
 
• Guidelines for the management of IRRs are provided in Section 5.1.1.1. In case of Grade 4 IRRs or anaphylaxis, study treatment should be permanently discontinued.
 

Clinical and laboratory TLS	
Grade 4 events:
 
 
• Permanently discontinue study treatment in the case of Grade 4 events.
 
 
Grade <math>\leq 3</math> events:
 
 
• Withhold study treatment. a
 
• Correct electrolyte abnormalities, monitor renal function and fluid balance, and administer supportive care, including dialysis as indicated.
 
• If symptoms (laboratory and clinical) have resolved completely, resume obinutuzumab or rituximab at full dose and resume venetoclax and idasanutlin at current dose.
 

New-onset neurologic manifestations suggestive of PML	
 
• Withhold study treatment. a
 
• Consult with a neurologist if PML is suspected (refer to Section 5.1.1.5 for guidance on investigations).
 
• If PML is ruled out, resume obinutuzumab or rituximab at the full dose and resume idasanutlin and venetoclax at the current dose.
 
• If PML is confirmed, permanently discontinue study treatment.
 

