**Table 18 Guidelines for Management of Non-Hematologic Toxicities (cont.)**

Event	Action to Be Taken
Diarrhea (cont.)	
Grade 2 or 3 diarrhea:
 
 
• If Grade 3 diarrhea occurs between Days 1 and 5 of the treatment cycle, withhold study treatment only if diarrhea does not improve to Grade <math>\leq 2</math> within 48 hours with appropriate treatment. After the study treatment is withheld, if diarrhea improves to Grade <math>\leq 2</math>, resume obinutuzumab or rituximab at the full dose and resume idasanutlin and venetoclax at a reduced dose according to guidelines in Sections 5.1.8.1 and 5.1.8.2 for current and subsequent cycles.
 
• If Grade 3 diarrhea is present at the time of the next planned cycle, withhold study treatment. If diarrhea improves to Grade <math>\leq 2</math>, resume obinutuzumab or rituximab at full dose and resume idasanutlin and venetoclax at a reduced dose according to guidelines in Sections 5.1.8.1 and 5.1.8.2 for current and subsequent cycles.
 
 
Management for diarrhea:
 
 
• Rule out other or concomitant causes, including, but not limited to, medications, Clostridium difficile infection, malabsorption/lactose intolerance, fecal impaction, and dietary supplements high in fiber.
 
• Initiate treatment at the time of onset.
 
• Administer loperamide 4 mg as loading dose; and up to 2 mg every 4 hours or after every unformed stool (for a maximum daily dose of 16 mg), or per institutional standard.
 
• For subsequent episodes, use 4 mg QD prophylactic loperamide 30 minutes before subsequent dosing. If diarrhea persists after 48 hours despite administration of the maximum recommended daily loperamide dose (16 mg/24 hr), second-line agents may be considered (diphenoxylate, atropine, octreotide, budesonide, or tincture of opium). Encourage patients to hydrate abundantly and self-medicate with loperamide 2 mg in the event that diarrhea recurs (up to 2 mg every 4 hours or after every unformed stool for a maximum daily dose of 16 mg), or per institutional standard.
 
• Monitor electrolyte levels closely and correct as appropriate.
 
• Administer IV fluids as clinically indicated.
 
• Upon presentation of Grade 3 diarrhea or diarrhea persists for >24 hours despite maximum recommended daily loperamide dose, exclude presence of active infections (e.g., C difficile). If present, treat infection(s), according to local guidelines.
 

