**Table 19 Guidelines for Management of Toxicities That Occur during Maintenance or Consolidation Treatment**

Event	Action to Be Taken
Hematologic toxicity: Grade 3 or 4	

• Withhold study treatment.

• Administer myeloid growth factors for neutropenia as allowed according to institutional guidelines.

• Administer RBCs or platelets as required.

• If improvement to Grade <math>\leq 2</math>, resume obinutuzumab or rituximab at full dose and resume venetoclax at next lower dose for subsequent cycles per guideline in Section 5.1.8. Patients who are not eligible for further venetoclax dose reductions should be permanently discontinued.

• If study treatment is withheld for <math>> 42</math> days, permanently discontinue study treatment.

• Withdraw venetoclax and idasanutlin in case of recurrent episodes of Grade <math>\geq 3</math> thrombocytopenia and/or neutropenia.

Non-hematologic toxicity: Grade $\geq 2$	

• Withhold study treatment.

• If improvement to Grade <math>\leq 1</math> or baseline, resume obinutuzumab or rituximab at full dose and resume venetoclax at the next lower dose for subsequent cycles per guideline in Section 5.1.8. Patients who are not eligible for further venetoclax and/or idasanutlin dose reductions should be permanently discontinued.

• If study treatment is withheld for <math>> 42</math> days, permanently discontinue study treatment.

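### After induction, Section 4.6.2 stops treatment for a related life-threatening non-hematologic event, but Table 19 says to resume on recovery and makes no exception for such an event

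*Protocol*

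**What the plan says.** Protocol Section 4.6.2 lists events after which study treatment should end permanently. One is a Grade 3 or higher "non-hematologic adverse event that has a reasonable possibility of being related to study treatment and either is life threatening or does not resolve to Grade" below 2 within 21 days. The list names a phase only for DLTs, which it ties to dose escalation.

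Table 19 (Section 5.1.8.2) covers maintenance and consolidation. Its non-hematologic row starts at Grade 2 and has no upper grade. Treatment is withheld. On improvement to Grade 1 or lower, or to baseline, sites "resume obinutuzumab or rituximab at full dose and resume venetoclax at the next lower dose for subsequent cycles". The row has two permanent-stop rules: more than 42 days withheld, and "Patients who are not eligible for further venetoclax and/or idasanutlin dose reductions should be permanently discontinued".

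Two passages direct the reader. Section 5.1 says: "Guidelines for managing adverse events, including criteria for dosage modification and treatment delays or discontinuation, are provided in Section 5.1.8". Section 5.1.8, below Table 15, says: "Guidelines for management of toxicities during induction treatment are provided in Section 5.1.8.1 and during consolidation or maintenance treatment in Section 5.1.8.2".

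**The concern.** The two texts give opposite instructions for the same patient: someone in maintenance or consolidation who has a related, life-threatening non-hematologic event and recovers. Section 4.6.2 ends treatment. Table 19, followed as written, restarts the antibody at full dose and venetoclax one level down.

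This is first a patient-safety rule. Two sites could act in opposite ways on the same event and each cite the protocol. It also touches reporting. Section 6.2 of the protocol tabulates treatment discontinuation for reasons other than progression, and SAP Outputs 5, 26 and 40 summarise post-induction drug completion, exposure and adverse events leading to discontinuation. Those summaries would mix patients managed under two rules.

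**Working it through.** No formula applies to the conflict itself. The check sets the texts side by side and asks whether any wording reconciles them.

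**1. The two rules**

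| | Section 4.6.2 | Table 19, non-hematologic row |
|---|---|---|
| Phase | None stated for this rule | Maintenance or consolidation |
| Grade | 3 or higher | 2 or higher, no upper limit |
| Life-threatening event | Permanent stop if related | Not mentioned |
| On recovery | No restart | Restart at Grade 1 or lower, or baseline |
| Cross-reference to the other | None | None |

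**2. Is Section 4.6.2 confined to induction?** No. Its other triggers, such as progression, pregnancy and Hy's Law cases, plainly apply after induction. Where the authors wanted an induction limit they wrote one: Section 5.1.8 ties its 21-day delay limit to induction.

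**3. Do life-threatening events fall inside the Table 19 row?** Yes. The row has no upper grade. Table 20, used for events not listed in the CTCAE, places life-threatening consequences at Grade 4.

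**4. A case that isolates the conflict.** Take a related Grade 4 non-hematologic event in maintenance that falls to Grade 1 within 21 days, with treatment withheld from onset until recovery and a venetoclax reduction still available. The 21-day non-resolution criterion is not met. Days withheld are at most 21, and 21 is below 42, so neither Table 19 stop applies. Section 4.6.2 still stops the patient, because the event was life threatening. Table 19 restarts the patient.

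**5. Does another passage supply the stop after induction?** Table 18 says "Permanently discontinue study treatment for Grade 4 events", but Section 5.1.8.1 introduces it with "Guidelines for management of non-hematologic toxicities that occur during induction treatment are presented in" Table 18. Against that, the table's title names no phase, and its diarrhea row says to "resume idasanutlin and venetoclax at a reduced dose according to guidelines in Sections 5.1.8.1 and 5.1.8.2 for current and subsequent cycles". Its nausea and vomiting row cites Section 5.1.8.2 as well. Its reach beyond induction is unclear, so it cannot be relied on to fill the gap.

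**6. Does the single-drug provision in Section 4.6.2 reconcile them?** Only in part. It lets the other drugs continue when toxicity is solely attributable to one drug, for patients with clinical benefit, after discussion with the Medical Monitor. Table 19's restart of both antibody and venetoclax carries no such condition.

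**7. Exposure at issue** (Tables 2 and 5; Appendix 1, treatment administration). Idasanutlin and venetoclax run for 6 months after induction in both diseases. Obinutuzumab in FL runs for 24 months, so 24 − 6 = 18 months are obinutuzumab alone.

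**8. Endpoints.** DLTs are counted in the first two cycles. Entry to post-induction treatment depends on the response at end of induction, so CR at EOI is settled before Table 19 applies.

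**The case against.** The strongest reply is that both texts can be followed. Section 4.6.2 is a stop list for the whole study; Table 19 manages patients who are still eligible for treatment. Once a stop criterion is met there is nothing to resume. The row also omits anaphylaxis and Hy's Law cases, and nobody would read that as leave to restart after them. For hematologic events Section 4.6.2 defers to Section 5.1.8, whereas for non-hematologic events it states its own criterion, which suggests that it governs. This is the sensible reading, and most investigators would probably reach it. But the order is inferred rather than stated. Table 19 lists its own permanent stops, so it looks complete, and it is where the protocol sends a site after induction.

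There are also general safeguards. Section 5.1.8 makes dosing conditional on acceptable clinical and laboratory findings, the investigator or sponsor may withdraw a patient, and the IMC reviews cumulative safety data. These lower the chance of harm. None of them corrects the instruction to resume.

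A reader might infer a second conflict, between the 21-day non-resolution limit in Section 4.6.2 and the 42-day withholding limit in Table 19, for related Grade 3 or higher events that are not life threatening. The documents do not establish one. One limit counts time to resolution and the other counts time withheld, and they can be read together as whichever is reached first. Which limit should govern after induction is a clinical question for the sponsor.

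**Conclusion.** The inconsistency is real and narrow: a related, life-threatening non-hematologic event in maintenance or consolidation that recovers in time for Table 19 to allow a restart. It should be corrected because the rule protects patients and the correction is small.

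It would go too far to infer that the protocol intends re-dosing after such events, or that sites will do it. Section 4.6.2 says the opposite and carries no phase limit; the defect is that Table 19 does not repeat it or point to it. The finding does not extend to Grade 2 events, unrelated events, or non-life-threatening Grade 3 events resolved within 21 days.

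The number of patients affected cannot be given, because the documents report no post-induction rate for these events. The effect on the analysis is limited to the descriptive post-induction safety and exposure summaries. The conclusion rests on reading Section 4.6.2 as applying in all phases and on Table 18's Grade 4 stop not clearly reaching past induction.

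**What to change.** Add one line to the non-hematologic row of Table 19: *Permanently discontinue study treatment for any related life-threatening (Grade 4) non-hematologic event (see Section 4.6.2); the single-drug provision in Section 4.6.2 still applies.*

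Avoid a broader line that imports every Section 4.6.2 criterion. That would bring in the criterion for a delay of more than 21 days in starting the next cycle, and so override the 42-day limit in Table 19. The sponsor should decide separately which of the 21-day and 42-day limits governs related Grade 3 or higher events that are not life threatening after induction.

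The cost is one line of protocol wording and no new procedure. A few patients may stop post-induction treatment who would otherwise have resumed under Table 19.

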#### **4.6.3 Study and Site Discontinuation**

The Sponsor has the right to terminate this study at any time. Reasons for terminating the study may include, but are not limited to, the following:

- The incidence or severity of adverse events in this or other studies indicates a potential health hazard to patients.
- Patient enrollment is unsatisfactory.

The Sponsor will notify the investigator if the Sponsor decides to discontinue the study.

The Sponsor has the right to close a site at any time. Reasons for closing a site may include, but are not limited to, the following:

- Excessively slow recruitment
- Poor protocol adherence
- Inaccurate or incomplete data recording
- Non-compliance with the International Council for Harmonisation (ICH) guideline for GCP
- No study activity (i.e., all patients have completed the study and all obligations have been fulfilled)

## **5. ASSESSMENT OF SAFETY**

### **5.1 SAFETY PLAN**

The safety plan for patients in this study is based on clinical experience with study treatment components in completed and ongoing studies. The anticipated important safety risks of IMPs in this study (i.e., obinutuzumab, rituximab, idasanutlin, and venetoclax) are outlined below. Please refer to the Obinutuzumab, Rituximab, Idasanutlin, and Venetoclax Investigator's Brochures for a complete summary of safety information.

Several measures will be taken to ensure the safety of patients participating in this trial. Eligibility criteria have been designed to exclude patients at higher risk of toxicities (see Section 4.1). In addition, patients will undergo adequate safety monitoring during the study, as described in this section and in Section 4.5. Guidelines for managing adverse events, including criteria for dosage modification and treatment delays or discontinuation, are provided in Section 5.1.8.

#### **5.1.1 Risks Associated with Obinutuzumab**

As of 4 July 2016, the following adverse events are considered to be important risks associated with obinutuzumab: IRRs, TLS, neutropenia (including prolonged and late-onset neutropenia), prolonged B-cell depletion, thrombocytopenia (including acute thrombocytopenia), infections (including PML and HBV reactivation), impaired immunization response, worsening of preexisting cardiac conditions, GI perforation, immunogenicity, and second malignancies. These events, with the exception of prolonged B-cell depletion, immunogenicity, and second malignancies, are described below.

##### **5.1.1.1 Infusion-Related Reactions**

IRRs have been reported predominantly during the first infusion of obinutuzumab. The incidence and severity of IRRs decreased substantially with the second and subsequent infusions. In the majority of patients, IRRs were mild or moderate and resolved with the slowing or interruption of the infusion and supportive care. The commonly experienced IRRs have been characterized by hypotension, fever, chills, flushing, nausea, vomiting, hypertension, fatigue, and other symptoms.

IRRs may be clinically indistinguishable from IgE-mediated allergic or anaphylactic reactions; anaphylaxis has been reported in patients treated with obinutuzumab.

Hypotension may occur during obinutuzumab IV infusions. Therefore, withholding of anti-hypertensive treatments should be considered for 12 hours prior to and throughout each obinutuzumab infusion and for the first hour after administration. Patients at acute risk of hypertensive crisis should be evaluated for the benefits and risks of withholding their antihypertensive medication.

Patients who have preexisting cardiac or pulmonary conditions should be monitored carefully throughout the infusion and the post-infusion period.

Guidelines for medical management of IRRs and anaphylaxis are provided in Section 4.3.2.1 and [Appendix 10](#).

### **5.1.1.2 Tumor Lysis Syndrome**

TLS, including fatal events, has been reported with obinutuzumab administration. Patients at risk of TLS (e.g., because of bulky disease or renal insufficiency) should receive adequate hydration and premedication with allopurinol or an alternative uricostatic agent as indicated in Section 4.3.2.5 (see [Table 8](#)). Additional guidelines for management of TLS in this study are provided in Section 5.1.6.

### **5.1.1.3 Neutropenia**

Grade 3 or 4 neutropenia, including febrile neutropenia, has been reported with obinutuzumab administration. Neutropenia resolved spontaneously or with use of hematopoietic growth factors. Patients who experience Grade 3 or 4 neutropenia should be closely monitored until neutrophil values return to at least Grade 2. Cases of late-onset neutropenia (ANC < 1000 cells/ $\mu$ L occurring  $\geq$  28 days after obinutuzumab treatment has been completed or stopped) or prolonged neutropenia (ANC < 1000 cells/ $\mu$ L) that does not resolve after 28 days without obinutuzumab treatment have also been reported. Prophylactic treatment with antibiotics should be administered as per standard practice. The use of G-CSF is allowed for treatment of neutropenia in this study. Guidelines for *treatment and* primary prophylaxis with G-CSF are provided in Section 4.4.1.

### **5.1.1.4 Thrombocytopenia**

Severe and life-threatening thrombocytopenia, including acute thrombocytopenia (occurring within 24 hours after the infusion), has been observed during treatment with obinutuzumab. In patients with CLL exposed to obinutuzumab, fatal hemorrhagic events have also been reported during Cycle 1. A clear relationship between thrombocytopenia and hemorrhagic events has not been established. Patients receiving concomitant medication that could possibly worsen thrombocytopenia-related events (e.g., platelet inhibitors and anticoagulants) may be at greater risk of bleeding and will not be included in the study. Patients should be closely monitored for thrombocytopenia, especially during the first cycle. For patients who experience thrombocytopenia, regular laboratory tests should be performed until the event resolves, and dose delays should be considered in case of severe or life-threatening thrombocytopenia. Transfusion of blood products (i.e., platelet transfusion) may be performed at the discretion of the treating physician, according to institutional practice.

